### 2 \* Discuss the research design including but not limited to such issues as: probability of group assignment, potential for subject to be randomized to placebo group, use of control subjects, etc.:

The study is a 12-week, double-blind, placebo-controlled, randomized clinical trial of the efficacy of anti-inflammatory combination therapy for the treatment of people with schizophrenia, who present with persistent positive symptoms.

There will be a 4-week evaluation phase during which baseline symptom, safety, laboratory, and neuropsychological assessments will be collected. Participants who continue to fulfill entry criteria will be entered into the 12-week Double-blind Treatment Phase.

Participants will be randomly assigned to salsalate, statin, and omega-3-fatty acid combination therapy (n=30) or placebo (n=30) using a permuted block randomization system. Treatment assignment order is random within each block, with an equal number of participants assigned to each treatment. The block sizes will vary in random sequence between 2 and 4. The salsalate target dose will be 4 gm/day, administered in two divided doses of 2 gm in the morning and 2 gm in the evening. The fluvastatin target dose will be 40 mg/day. We selected fluvastatin because it does not interfere with the metabolism of risperidone and paliperidone (two widely used antipsychotics), and it crosses the blood brain barrier. We will use a combined omega-3-fatty acid preparation of EPA and DHA in a 1gm capsule. Each 1gm capsule will contain 180.9mg of EPA and 120.6mg of DHA in doses of two capsules in the morning and two capsules in the evening (2g omega-3-fatty acid in the morning and 2g omega-3-fatty acid in the evening).

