- 6) Columbia Suicide Severity Rating Scale (C-SSRS): The C-SSRS is a questionnaire used for suicide assessment at screening and during the course of treatment.

The primary evaluators will administer the BPRS, SANS, Calgary Depression Scale (CDS) and CGI-S at the beginning of the Evaluation Phase and bi-weekly thereafter. The FTND will be administered at the beginning and end of the Treatment Phase.

B. Neuropsychological Assessments: The MATRICS Consensus Cognitive Battery (MCCB) will be used to assess neuropsychological test performance. All participants will receive this portion of the assessments at MPRC.

C. Side Effects: Side Effect Checklist (SEC); the SEC is designed to assess vital signs and commonly occurring medication-related side effects. EKG and Vital Signs will also be monitored. At MPRC, the Side-Effect Checklist (SEC) and vital signs will be administered at treatment baseline and bi-weekly thereafter by a non-blind clinical pharmacist, who will not disclose the results to treatment/rating clinicians.

D. Laboratory: All patients will receive these assessments at MPRC. If laboratory abnormalities occur, repeat labs may be performed on visits where they are unscheduled in the assessment schedule. This will be determined by a study physician.

- 1) Safety: CBC; complete metabolic panel (CMP), including electrolytes, BUN, creatinine, fasting blood glucose, liver function tests, and lipid profile; U/A; pregnancy test; vital signs.
- 2) Cytokine profile: IL-1 $\beta$ , IL-1RA, IL-2, sIL-2R, IL-6, IL-10, IL-12, IL-17, CRP, IFN- $\gamma$ , TNF- $\alpha$ , and TGF- $\beta$ .

E. Other: We will collect blood for peripheral blood mononuclear cells (PBMC) cultures, which will be used to evaluate in vitro lipopolysaccharide-induced cytokine production. The use of PBMC cultures complements the collection of peripheral cytokine measures. The latter may be vulnerable to differential concentrations between the site of cytokine release and blood concentrations and the relatively short half-life of cytokines.

- 2 \* Describe all procedures already being performed for diagnostic or treatment purposes (if not applicable to the study, enter "N/A"):

The procedures in this protocol are conducted for research purposes.

- 3 \* Describe the duration of an individual participant's participation in the study:

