There will be a 4-week evaluation phase during which baseline symptom, safety, laboratory, and neuropsychological assessments will be collected. Participants who continue to fulfill entry criteria will be entered into the 12-week Double-blind Treatment Phase. Hence entire duration of participation for the participant is 16 weeks.

- 4 \* Describe the duration of the entire study:

We anticipate that the duration of this study will be three years.

- 5 \* Describe any additional participant requirements:

None

ID: VIEW4E0280585B40  
Name: v2\_Study Procedure

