## Sample Size and Data Analysis

**If you uploaded a separate research protocol document in the 'Research Protocol' page, cite the applicable section and page numbers from that document in the answer boxes below.**

- 1 \* Provide the rationale and sample size calculations for the proposed target population:

Power for analyses:

Specific Aim 1: Based on similar MPRC studies of adjunctive treatments, we anticipate approximately a 10% dropout rate. In previous trials of similar length, we have found that the correlation,  $r$ , between baseline and follow-up scores is approximately  $r=0.6$ . The effect size,  $d/\sigma$ , detectable from this study can be estimated from the formula  $(d/\sigma)^2 = 2(\alpha + z\beta)^2(1-r^2)/n$ , where  $d$  is the MM-ANCOVA difference estimate at week 8,  $\sigma$  the standard deviation at week 8,  $z\beta = 0.84$  and  $\alpha = 1.96$  are the standard normal percentiles corresponding to power=0.80 and  $\alpha=0.05$  (two-sided). We would have power to detect an effect size:  $d=0.61$ .

Specific Aim 2: The correlation,  $r$ , between baseline and follow-up MCCB composite scores has now been reported in multiple clinical trials to be  $r>0.9$ . Substituting this value for  $r$  into the ANCOVA power formula given above, we should have power=0.80 to detect an effect size:  $d=0.33$  on the MCCB total score.

- 2 \* Provide the plan for data analysis. Include in the description the types of comparisons that are planned (e.g., comparison of means, comparison of proportions, regressions, analysis of variance, etc.), which is the primary comparison/analysis, and how the analyses proposed will relate to the primary purposes of the study:

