Specific Aim #1: The effect of combined anti-inflammatory treatment versus placebo on persistent positive symptoms will be tested using the mixed model for repeated measures analysis of covariance (MM-ANCOVA): follow-up score = baseline score + study week + treatment x study week, where "study week" represents a set of binary indicators of whether the follow-up measurement comes from weeks 2, 4, 6, or 8; the main effect of treatment in this model is the average (across weeks 2, 4, 6, and 8) adjusted (for baseline score) difference in follow-up scores between anti-inflammatory treatment and placebo, while the treatment x week interaction tests for significant variation among follow-up weeks in the magnitude of the treatment effects. The primary outcome tested from this model will be a post hoc estimate of the treatment difference at week 8; exploratory analysis of the average treatment effect across weeks and changes in the magnitude of the treatment effect over time will also be conducted.

Specific Aim #2: The primary test for treatment effects on cognition will be performed using the MCCB composite score and the ANCOV A model follow-up composite score = baseline composite score + treatment. Exploratory analyses examining treatment effects for specific domains will be analyzed using the MM-ANCOV A model: follow-up domain T -score = baseline domain T -score + domain + treatment x domain, where the treatment x domain interaction term provides an overall test for variation in the magnitude of anti-inflammatory - placebo T -differences across domains, and the effects of anti-inflammatory treatments in specific domains can be estimated by post-hoc tests from this general model.

Secondary outcomes:

- 1) Treatment differences on clinical symptom outcomes (CDS depression, SANS negative symptom score) will be assessed with MM-ANCOV A, using models similar to that prescribed for analyses of positive symptoms.
- 2) Treatment differences on side effects will be assessed by comparing the proportion of participants in each group with either new onset or worsening compared to baseline for each of a list of specified side effects, using Fisher's exact test.

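### The primary model stops at week 8 of a 12-week treatment phase, without a stated reason, so the end-of-treatment effect is not estimated

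*Combined protocol and SAP*

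**What the plan says.** **Design.** Justification, Objective, & Research Design, item 2: "The study is a 12-week, double-blind, placebo-controlled, randomized clinical trial". Study Procedures, item 3: "Participants who continue to fulfill entry criteria will be entered into the 12-week Double-blind Treatment Phase". A 4-week evaluation phase comes first, giving 16 weeks in all.

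**Ratings.** Study Procedures, item 1, has the BPRS, SANS, CDS and CGI-S administered "at the beginning of the Evaluation Phase and bi-weekly thereafter".

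**Analysis.** Sample Size and Data Analysis, item 2, Specific Aim #1, defines study week as "a set of binary indicators of whether the follow-up measurement comes from weeks 2, 4, 6, or 8". The exploratory average effect covers the same four weeks. The primary test is stated thus: "The primary outcome tested from this model will be a post hoc estimate of the treatment difference at week 8". CDS and SANS are to be analysed with models similar to the one for positive symptoms.

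**Power.** In item 1 of that section, d "is the MM-ANCOVA difference estimate at week 8", and the standard deviation is also the week-8 value.

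**The concern.** The design sections describe 12 weeks of treatment, but the statistical section describes a model that ends at week 8. Week 8 appears in the model, the primary contrast and the power text, so this is not one slip of the pen. No section explains the choice or says what will be done with later symptom ratings.

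The primary conclusion would therefore be drawn at two-thirds of the planned exposure (8/12). A reader of the results would expect the effect after the full 12 weeks, and the specified model has no term for it. If both week 8 and week 12 results exist at the end and the plan fits the design badly, there is also room to argue about which one counts. CDS and SANS would probably inherit the same limit.

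**Working it through.** **1. Which ratings does the schedule imply?** Ratings start with the evaluation phase and recur every two weeks. Counted from the start of treatment, the post-baseline ratings fall at weeks 2, 4, 6, 8, 10 and 12: six in all. The model names four, so 2 of 6 (33%) are not placed.

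Counting weeks from the start of the evaluation phase does not remove the mismatch. Weeks 2 and 4 would then fall within the 4-week evaluation phase, and week 8 would be treatment week 4.

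**2. Does the plan's power figure reproduce?** Inputs from Sample Size and Data Analysis, item 1: z values 1.96 and 0.84, r = 0.6, dropout 10%. The research design section gives 30 per arm, so n = 30 × 0.90 = 27.

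d/σ = √[2(1.96 + 0.84)²(1 − r²)/n] = √[2 × 7.84 × 0.64/27] = 0.6097

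This matches the stated 0.61. With 30 per arm the result would be 0.578, so the stated figure already allows for dropout.

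**3. What happens if the primary contrast moves to week 12?** The formula has no time term. With r = 0.6 and 27 per arm the detectable effect is still 0.61. The documents give no r or dropout specific to week 12, so every row below except the first rests on assumed values.

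| r | Dropout (n per arm) | Detectable effect, SD | Power at 0.61 SD |
|---|---|---|---|
| 0.6 | 10% (27) | 0.61 | 80.0% |
| 0.5 | 10% (27) | 0.66 | 73.5% |
| 0.6 | 20% (24) | 0.65 | 75.2% |
| 0.5 | 20% (24) | 0.70 | 68.4% |

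**4. What could testing at week 8 cost?** This is an illustration only. Suppose the effect is 0.61 SD at week 12 and a fraction f of it is present by week 8. The standard error is √(2 × 0.64/27) = 0.2177, and power = Φ(f × 0.61/0.2177 − 1.96).

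- f = 1 (plateau by week 8): 80%
- f = 0.90: 71%
- f = 0.75: 56%
- f = 2/3 (linear growth, 0.41 SD at week 8): 46%

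The documents give no time course for the effect, so no value of f can be preferred.

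**5. Do the other outcomes follow the same clock?** The MCCB and cytokine analyses name no week. Prospective Samples, item 2, places the on-treatment blood draws at the beginning and end of the treatment phase. Cytokine change would therefore run to the end of treatment, while the primary symptom contrast is at week 8.

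**The case against.** A week-8 primary contrast in a 12-week trial is permissible if it is chosen in advance and explained. The aims name no time point, and week 8 is used consistently in the power and analysis text. That stands: the fault is an unexplained mismatch, and a justified week 8 could be defended. No justification is given, however, and even a justified week 8 would leave weeks 10 and 12 without a stated place in the symptom models.

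The ratings at weeks 10 and 12 are themselves inferred from the two-weekly schedule and the phase length. Additional Documents lists an assessment schedule and a fuller protocol that are not reproduced here. The inference is sound on the text available, but the sponsor should confirm it.

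A reader might infer more than the documents support:

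- *That the late ratings are discarded.* The plan never says so; it only gives them no place in the models. The Spearman correlations of symptom change name no week and could use them. CDS and SANS get similar models, not expressly identical ones.
- *That the stated 80% power is wrong.* It is right for the plan's own target, 0.61 SD at week 8. The figures of 71%, 56% and 46% move that target to week 12 under assumed time courses. Moving the contrast could also cost power if r is lower or dropout higher at week 12.
- *That everyone contributes 12 weeks of data.* The plan expects about 10% dropout and has withdrawal rules. The ratings are scheduled, not assured.
- *That week 8 is left over from a shorter design.* The salsalate entry in Research Related Risks does mention use for 6 weeks, another duration that differs from 12, but this does not establish where week 8 came from.

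**Conclusion.** The concern holds as a contradiction between the design and the analysis. Treatment runs for 12 weeks, while the primary model, contrast and power inputs end at week 8 with no reason given. If the plan is followed as written, the end-of-treatment effect on positive symptoms is not estimated by the specified model, and 2 of the 6 implied post-baseline ratings have no stated place in the symptom models. CDS and SANS would probably be affected in the same way.

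The conclusion rests on the two-weekly schedule continuing through the 12-week phase. It does not rest on any assumed growth of the effect, and it does not question the sample size. Because it concerns the primary contrast, it should be settled before any results by arm are known.

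**What to change.** In Sample Size and Data Analysis:

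1. Define study week as 2, 4, 6, 8, 10 and 12, in the model and in the exploratory average.
2. Make the week-12 treatment difference the primary contrast and keep week 8 as secondary. Call the primary contrast pre-specified instead of post hoc.
3. State the same weeks and contrast for CDS and SANS.
4. Restate the power text for week 12, and either support r = 0.6 and 10% dropout at that week or show the range in the table above.

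If the sponsor keeps week 8 as primary, the plan should give the reason and still model weeks 10 and 12, so that the end-of-treatment effect is reported.

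The cost is an amendment. If the ratings at weeks 10 and 12 are taken as the schedule implies, no new visits are needed, and under the plan's own inputs the sample size does not change.

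The amendment needs care. Funding Information refers to the final two participants, so the study appears to be at a late stage. Monitoring Plan - Committee lists outcomes and preliminary analyses among the data reviewed, and Monitoring Plan - Internal DSMB allows the study statistician to prepare unblinded reports when needed, although no interim efficacy analysis is planned. The amendment should be dated and should record that those who chose the time point had not seen results by treatment arm.

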### 1 \* Describe the purpose, specific aims, or objectives of this research. State the hypothesis to be tested:

Primary Aims:

1. To determine if adjunctive anti-inflammatory combination therapy is superior to placebo for persistent positive symptoms.
2. To determine if adjunctive anti-inflammatory combination therapy is superior to placebo for depressive and negative symptoms.

Secondary Aims:

1. To determine if adjunctive anti-inflammatory combination therapy compared to placebo is associated with increased incidence of side effects.
2. To determine if adjunctive anti-inflammatory combination therapy is superior to placebo for depressive and negative symptoms.
3. To determine if adjunctive anti-inflammatory combination therapy compared to placebo is associated with an improvement in the pro-inflammatory cytokines: interleukin (IL)-1 $\beta$ , IL-6, and Tumor Necrosis Factor (TNF)- $\alpha$ .

We hypothesize adjunctive anti-inflammatory combination therapy will be associated with improvements in depressive and negative symptoms and a reduction in pro-inflammatory cytokines. We hypothesize that no elevated adverse risk will be associated with adjunctive anti-inflammatory combination therapy relative to placebo.

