## Research Related Risks

If you uploaded a separate research protocol document in the 'Research Protocol' page, cite the applicable section and page numbers from that document in the answer box below.

- 1 \* Individually list each research-related risk, using a separate line for each. Next to each risk, delineate the likelihood/seriousness of the risk, and the provisions for minimizing the risk:

Salsalate:

1- Tinnitus. Somewhat likely and not serious. On a weekly basis, participants will undergo side effect checklist assessment of commonly occurring drug side effects, with a specific question included to address this side effect. If the participant is unable to tolerate the drug at the target dose of 4 grams per day then 500 mg reductions will be made in a stepwise fashion until the tinnitus remits or a minimum dose of 2 grams per day is reached.

2 - Headache. Not likely and not serious. On a weekly basis, participants will undergo side effect checklist assessment of commonly occurring drug side effects, with a specific question included to address this side effect.

3 - Dizziness. Not likely and not serious. On a weekly basis, participants will undergo side effect checklist assessment of commonly occurring drug side effects, with a specific question included to address this side effect.

4 - Nausea, dyspepsia, and the remote possibility of GI bleeding. Not likely and possibly serious. These are less common side effects and occur infrequently in individuals taking the drug for only 6 weeks. On a weekly basis, participants will undergo side effect checklist assessment of commonly occurring drug side effects, with specific questions included to address these side effects. If a participant develops GI bleeding the drug will be stopped immediately .

5 - Pregnancy risks. Somewhat likely and serious. There is some evidence with medications similar to Salsalate that an unborn child may have trouble with the heart forming correctly. If a woman is pregnant or planning on becoming pregnant she cannot participate in this study .

Fluvastatin:

1 - Headache. Somewhat likely and not serious. On a weekly basis, participants will undergo side effect checklist assessment of commonly occurring drug side effects, with a specific question included to address this side effect.

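### The expectation of no excess side-effect risk is assessed only by item-by-item Fisher tests with about 30 per arm, whose non-significance cannot support it; report risk differences with intervals instead

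*Combined protocol and SAP*

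**What the plan says.** All references are to the combined protocol and SAP.

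- **Aim.** In Justification, Objective, & Research Design, item 1, the first secondary aim is: "To determine if adjunctive anti-inflammatory combination therapy compared to placebo is associated with increased incidence of side effects".
- **Hypothesis.** The same item then states: "We hypothesize that no elevated adverse risk will be associated with adjunctive anti-inflammatory combination therapy relative to placebo".
- **Analysis.** Sample Size and Data Analysis, item 2, second secondary outcome: "Treatment differences on side effects will be assessed by comparing the proportion of participants in each group with either new onset or worsening". Change is judged from baseline, and every listed item gets its own Fisher's exact test. The second copy of the application in the same file repeats it.
- **Size.** Participants are randomised to "combination therapy (n=30) or placebo (n=30) using a permuted block randomization system", and under Sample Size and Data Analysis, item 1, "we anticipate approximately a 10% dropout rate". Power is given there for Specific Aims 1 and 2 only.
- **Expected effects.** Research Related Risks rates several effects as somewhat likely. The first salsalate entry reads "Tinnitus. Somewhat likely and not serious", and it has its own dose rule: "500 mg reductions will be made in a stepwise fashion until the tinnitus remits".

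For side effects, the visible text gives no risk difference, confidence interval, margin, significance level or power. It also gives no rule for when the hypothesis counts as supported.

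**The concern.** The hypothesis is one of no excess, while the test is one of equality. Rejecting equality shows a difference. Failing to reject it shows only that the data did not rule equality out. With 30 per arm that happens often even when a side effect is materially more frequent on active treatment.

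At stake is the answer to a named secondary aim. The planned output is a pair of proportions and a p-value per item, with nothing on how large an excess the data leave open. A reader comparing non-significant p-values with the stated hypothesis would have little to stop them from concluding that the combination is as well tolerated as placebo.

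**Working it through.** **Inputs from the documents.** 30 randomised per arm; about 10% dropout, so 30 × 0.9 = 27 per arm; two-sided 0.05. That level is stated only for the efficacy power, and I assume it carries over to the Fisher tests.

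**Input assumed.** Placebo rates for the side effects: none is given, so I scan 0, 5, 10, 20 and 30%.

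**1. The plan's own power figure.** For Aim 1, with r = 0.6 and n = 27: d = √[2(1.96 + 0.84)²(1 − 0.6²)/27] = √(10.035/27) = 0.61, as stated. There is no corresponding figure for side effects to reproduce.

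**2. Power of one Fisher test.** With placebo rate p and true rise Δ, sum over all pairs of counts:

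Power = Σₓ Σᵧ Bin(x; n, p + Δ) · Bin(y; n, p) · 1[Fisher p(x, y) ≤ 0.05]

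| Placebo rate | +15 points, n = 30 | +20 points, n = 30 | +15 points, n = 27 | +20 points, n = 27 |
|---|---|---|---|---|
| 0% | 29% | 57% | 21% | 46% |
| 5% | 24% | 44% | 19% | 36% |
| 10% | 21% | 37% | 17% | 31% |
| 20% | 18% | 30% | 15% | 26% |
| 30% | 15% | 26% | 14% | 23% |

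The chance of a miss is one minus these figures. At 30 per arm it is 71 to 85% for +15 points. For +20 points it is 56 to 74% at placebo rates of 5 to 30%, and 43% at a rate of zero.

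**3. Rise needed for 80% power at 30 per arm.** About 26, 31, 34, 38 and 39 points at placebo rates of 0, 5, 10, 20 and 30%.

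**4. Sensitivity to sidedness.** If the tests were one-sided at 0.05, power at 30 per arm for +15 points would be 48, 36, 31, 27 and 23% over the same rates, still below one half throughout. For +20 points it would be 75, 57, 49, 42 and 36%.

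**5. What an interval adds.** The Miettinen-Nurminen interval contains every difference δ for which |p̂₁ − p̂₀ − δ| / √[V(δ) · N/(N − 1)] ≤ 1.96. Here N = 60, and V(δ) is the variance at the maximum-likelihood rates constrained to differ by δ.

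| Active vs placebo | Fisher p | Difference, points | 95% interval, points |
|---|---|---|---|
| 3/30 vs 3/30 | 1.00 | 0 | −17.5 to +17.5 |
| 8/30 vs 3/30 | 0.18 | +16.7 | −3.3 to +36.5 |
| 10/30 vs 3/30 | 0.057 | +23.3 | +2.5 to +43.4 |
| 5/30 vs 0/30 | 0.052 | +16.7 | +4.2 to +33.7 |

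All four are non-significant by Fisher's test. In the last two the interval lies wholly above zero. In the first, p = 1.00 is still compatible with an excess of about 17 points.

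**The case against.** **The test fits the aim.** The aim asks whether side effects increase, and comparing proportions addresses that. The no-excess statement is a single sentence of expectation. This is fair, and it is why the test need not be discarded. But the sentence is labelled a hypothesis, and the only analysis that bears on it cannot support it.

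**The plan never equates non-significance with safety.** A reader might infer that it does. The documents do not say so. They leave that reading open and supply nothing to correct it.

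**The proportions will be visible anyway.** The plan compares proportions by arm, so 8/30 against 3/30 would be seen. What is missing is a statement of the excess that the data do and do not exclude.

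**A list is more informative than one item.** It is tempting to say that the results would look the same whether or not risk is raised. At a 10% placebo rate that is nearly true of one item: about 99% non-significant at equal risk, 79% at +15 points. It is not true of a list. For five independent items, all are non-significant with probability 0.9906⁵ = 95% at equal risk, against 0.787⁵ = 30% if every item rises by 15 points. Correlation, or a rise in one item only, narrows that gap.

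**Placebo rates are unknown and could be near zero.** Pre-existing tinnitus is an exclusion, so new tinnitus on placebo may be rare. At a zero rate and 30 per arm, +20 points is detected 57% of the time, so it would be wrong to say such a rise is usually missed at every rate. For +15 points it is.

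**The 27-per-arm figures may be too pessimistic.** Side effects are assessed repeatedly, so participants who drop out can still contribute events. The 30-per-arm figures are the ones to rely on.

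**The DSMB's 25% incidence trigger.** A reader might see it as contradicting the final test. It does not: it is an absolute monitoring threshold in either arm, not a comparison of arms.

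**Unseen material.** The side-effect list and an attachment titled Full Study Protocol, both named in the file, are not shown and could contain an interval or margin.

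**Conclusion.** The concern holds for how the no-excess hypothesis is to be assessed. At about 30 per arm, a non-significant Fisher test on one side effect cannot support it: a true 15-point rise would be missed 71 to 85% of the time, and a 20-point rise 56 to 74% of the time at placebo rates of 5 to 30% (43% at zero). These figures rest on assumed placebo rates, a two-sided 0.05 level carried over from the efficacy calculation, and all 30 per arm contributing.

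Low power for individual side effects is unavoidable in a trial of 60 and is not itself the fault. The fault is that the visible plan reports nothing that conveys it. The change could alter how tolerability is described; it does not touch the efficacy result.

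**What to change.** Replace the Fisher sentence with text such as:

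> For each specified side effect we will report n/N by arm among all randomised participants who took at least one dose, with the risk difference (active minus placebo) and its 95% Miettinen-Nurminen interval as the main result. Fisher p-values are descriptive. A non-significant p-value will not be read as evidence of no elevated risk. Conclusions will be worded from the interval, stating the size of excess it does and does not rule out.

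A formal margin is optional. The documents offer no basis for one; if the clinical team wants it, they should choose it and fix it before unblinding.

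**Cost.** A few sentences and one table layout, with no new data, visits or staff. The intervals will be wide (about −17 to +17 points for 3/30 against 3/30), so many items will read as inconclusive. About 2.5% of unaffected items will show an interval wholly above zero, because nothing is adjusted for the number of items. Both should be acknowledged in the report.

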Treatment Phase: Participants who continue to fulfill entry criteria will be entered into the 12-week Double-blind Treatment Phase, in which participants will be randomly assigned to salsalate, fluvastatin, and omega-3-fatty acid combination therapy (n=30) or placebo (n=30) using a permuted block randomization system. Treatment assignment order is random within each block, with an equal number of participants assigned to each treatment. The block sizes will vary in random sequence between 2 and 4. The salsalate target dose will be 4 gm/day, administered in two divided doses of 2 gm in the morning and 2 gm in the evening. The fluvastatin target dose will be 40 mg/day. Participants randomized to fluvastatin will receive placebo fluvastatin in the morning and active drug in the evening. We selected fluvastatin (because it does not interfere with the metabolism of risperidone and paliperidone (two widely used antipsychotics), and it crosses the blood brain barrier. We will use a combined omega-3-fatty acid preparation of EPA and DHA in a 1gm capsule. Each 1gm capsule will contain 180.9mg of EPA and 120.6mg of DHA in doses of two capsules in the morning and two capsules in the evening (2g omega-3-fatty acid in the morning and 2g omega-3-fatty acid in the evening).

evening). We selected this dose of EP A and DHA, because these were the doses used in the Amminger et al. study ( No. 48, Summary of Supporting Literature section), which has, to date, produced the most profound results for this intervention.

Assessments: We will collect the following clinical, neuropsychological, safety, and laboratory assessments:

A. Clinical:

- 1) Brief Psychiatric Rating Scale (BPRS; Overall & Gorham, 1980): A 20-item scale of psychiatric symptoms rated from 1 (not present) to 7 (very severe).
- 2) Scale for the Assessment of Negative Symptoms (SANS): A 22-item scale designed to quantify the severity of negative symptoms in schizophrenia. Items are rated from 0 (not present) to 5 (severe).
- 3) Calgary Depression Scale (CDS): the CDS total score will be used to measure depressive symptoms. The CDS was specifically designed to assess depressive symptoms in people with schizophrenia.
- 4) CGI-Severity of illness (CGI-S): the CGI-S will be used to assess global changes.
- 5) Fagerstrom Test for Nicotine Dependency (FTND): the FTND will be used to document smoking status and to measure change in smoking status during the course of treatment.

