- 3) Treatment differences in changes in cytokine expression will be assessed using the Wilcoxon rank sum test to compare change scores on each cytokine measure. We anticipate many participants will have cytokine measurements below the limit of detection at one or both visits. For such participants, we will impute cytokine measurements equal to ½ the limit of detection for the assay.
- 4) Spearman rank correlations will be assessed between changes in symptoms and cognitive outcomes

ID: VIEW4E0280605280  
Name: v2\_Sample Size and Data Analysis

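### The cytokine test uses unadjusted change scores; under plausible assumptions a baseline-adjusted rank analysis of the same data has more power to detect the hypothesised reduction

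*Combined protocol and SAP*

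**What the plan says.** Sample Size and Data Analysis, Secondary outcomes item 3, states that cytokine differences "will be assessed using the Wilcoxon rank sum test to compare change scores on each cytokine measure". It adds: "We anticipate many participants will have cytokine measurements below the limit of detection at one or both visits". For those participants, "we will impute cytokine measurements equal to ½ the limit of detection for the assay". The item names no baseline covariate, transformation, censored-data method or sensitivity analysis.

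The same section puts the baseline score into the models for positive symptoms and the MCCB composite, and carries the positive-symptom approach over to CDS and SANS. Its power formula contains the factor (1-r²), which is the precision gained by adjusting for baseline.

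Secondary Aim 3 (Justification, Objective, & Research Design, item 1) asks whether treatment "is associated with an improvement in the pro-inflammatory cytokines" IL-1β, IL-6 and TNF-α, and the hypothesis is a reduction. Study Procedures, Laboratory item 2, lists twelve analytes.

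**The concern.** Cytokines are the one group of continuous outcomes compared between arms without baseline adjustment, and no reason is given. They are also the outcomes for which a change score carries least information. A participant below LOD at both visits scores exactly zero change whatever the treatment did. If values are skewed and change is taken on the raw scale, the ranks of change are driven largely by where the participant started.

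The rationale of the trial is that the drugs reverse a pro-inflammatory state, and item 3 is the analysis the plan specifies for that. If its power is needlessly low, a null result may be read as evidence that inflammation did not move.

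**Working it through.** **Inputs from the documents.** Allocation is "combination therapy (n=30) or placebo (n=30) using a permuted block randomization system" (Study Procedures), and "we anticipate approximately a 10% dropout rate" (Sample Size and Data Analysis), so n = 30 × 0.9 = 27 per arm. The section gives r = 0.6 for symptom scores, power 0.80 and two-sided α 0.05.

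**Assumed, because the documents are silent.** Cytokine baseline-to-follow-up correlation r from 0.3 to 0.9; share below LOD 0%, 30%, 50% or 70%; log-normal values with log SD 0.5 or 1; treatment lowering log values by about 0.6 SD.

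**Step 1: the plan's own figures.** d = √[2(1.96+0.84)²(1-r²)/n]. With n = 27 this gives √(2 × 7.84 × 0.64/27) = 0.61 at r = 0.6 and √(2 × 7.84 × 0.19/27) = 0.33 at r = 0.9. Both stated values reproduce. They are for symptoms and MCCB; no power figure is given for cytokines.

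**Step 2: no censoring, normal data.** The variance of a change score relative to ANCOVA is 2(1-r)/(1-r²) = 2/(1+r): 1.54 at r = 0.3, 1.25 at 0.6, 1.11 at 0.8 and 1.05 at 0.9. At r = 0.6 and d = 0.61, with the Wilcoxon factor √(3/π) = 0.977, the test on change has Φ(0.977 × 0.61/[√0.8 × √(2/27)] - 1.96) = Φ(0.49) = 69% power where ANCOVA has 80%. The corresponding figures at r = 0.3, 0.8 and 0.9 are 60%, 74% and 76%.

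**Step 3: skewed data with censoring.** Simulation with 27 per arm, 6,000 replicates, r = 0.6, log SD 1, effect 0.61 SD on the log scale, and values below LOD set to half the LOD at both visits. Rank ANCOVA regresses the rank of follow-up on the rank of baseline plus arm; Quade's test gives the same results.

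| Below LOD | Wilcoxon, raw change | Wilcoxon, log change | Rank ANCOVA |
|---|---|---|---|
| 0% | 50% | 66% | 74% |
| 30% | 42% | 52% | 66% |
| 50% | 33% | 38% | 55% |
| 70% | 23% | 24% | 40% |

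Type I error at r = 0.6 was 4.3% to 5.5% for all methods. At a fall of 0.6 SD the 50% row becomes 34% against 56%, a difference within simulation error.

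**Step 4: range over the assumptions.** Gain of rank ANCOVA over the raw-change Wilcoxon test for a fall of 0.6 SD, 30-50% below LOD, log SD 0.5 to 1:

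| r | Gain, points (about) |
|---|---|
| 0.3 | 20-24 |
| 0.6 | 16-24 |
| 0.8 | 11-19 |
| 0.9 | 5-16 |

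**Step 5: where the loss arises.** With nothing below LOD no substituted value enters, yet the gap in the Step 3 table is at its widest, 74 - 50 = 24 points. Of that, 66 - 50 = 16 points go with the raw scale and 74 - 66 = 8 remain on the log scale. At 50% below LOD, 38 - 33 = 5 points go with the scale and 55 - 38 = 17 remain. Rank ANCOVA does not depend on the value substituted below LOD, because all such values tie at the lowest rank. At 50% below LOD about 40% of participants have a change of exactly zero.

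**The case against.** The planned test is valid and the plan already foresees non-detects and states a rule for them. This is an efficiency question on a secondary aim. That stands, and it is why the point is an improvement and not an error.

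The size depends on quantities the documents do not contain; the 0.6 correlation is given for symptom scores. That also stands, so only a range can be reported.

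A reader might infer that the adjusted analysis can never do worse. The plan does not state the scale of change, and on the log scale with no censoring at r = 0.9 (effect rescaled to 0.33 SD) the Wilcoxon test has 74% power against 68%. On raw change with r = 0.95, log SD 0.3 and no censoring it has 70% against 66%. If treatment raised cytokines, at r = 0.9 with 70% below LOD, it has 87% against 81%. These settings depart from the hypothesised reduction with many non-detects, but they rule out a blanket claim.

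A reader might also blame the half-LOD substitution. Step 5 shows that it is secondary, and censoring lowers power for either method. A participant below LOD at baseline cannot show a fall under any analysis.

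Finally, testing each of twelve analytes might suggest a 46% chance of a false positive (1 - 0.95¹² = 0.46). That is an upper bound which assumes independent tests. With an assumed common correlation of 0.3, 0.5 or 0.7 it is 40%, 32% or 23%, and Secondary Aim 3 already names three cytokines.

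**Conclusion.** The concern holds as a recommended improvement to the analysis of Secondary Aim 3. For a reduction in cytokines with a substantial share below LOD, the unadjusted change-score test gives up power that the same data could supply: roughly 5 to 24 points at 30-50% below LOD, shrinking as the correlation rises. The direction is stable over r from 0.3 to 0.9 for a fall with 30-70% below LOD, on either the raw or the log scale. The size rests on assumed correlation, skewness, LOD share and effect.

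The documents do not support a claim that the planned test is invalid, that half-LOD substitution is the main cause, or that this is the only mechanistic measurement. Study Procedures also collects PBMC cultures for induced cytokine production, although no separate analysis of them is stated. The primary outcome is unaffected.

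**What to change.** In Sample Size and Data Analysis, Secondary outcomes item 3 (the text appears twice in the combined file; change both), make the main cytokine test a rank ANCOVA (Quade): rank the follow-up values with all below-LOD results tied at the lowest rank, adjust for the similarly ranked baseline, and compare arms. No substituted value is then needed. Keep the Wilcoxon test on change with half-LOD values as a sensitivity analysis, and state its scale.

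The cost is a few lines of text and slightly more analysis work, with no new data. The downside is a possible small loss of power if the correlation proves very high.

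Optional and separate: name IL-1β, IL-6 and TNF-α as the confirmatory set and label the other nine analytes exploratory.
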